11.0 CRITERIA FOR REMOVAL FROM THE STUDY

This will include:

1. Possibility of undergoing allogeneic bone marrow transplantation
2. Unacceptable adverse event(s)
3. Discontinuation of study drug for more than 6 weeks
4. Clinically significant intercurrent illness that prevents further administration of treatment
5. Patient request
6. General or specific changes in the patient's condition that render the patient unacceptable for further treatment in the judgment of the investigator or treating physician.
7. Note that patients with progressive disease or lack of objective response after 4 cycles of Pacritinib monotherapy are eligible to continue on study with the addition of a hypomethylating agent (azacitidine or decitabine) to Pacritinib. In patients with clinically significant progressive disease and/or lack of objective response after 4 cycles of *combination* therapy, treatment will be discontinued.

12.0 STATISTICAL CONSIDERATIONS

General Description

This is a Phase II open-label study designed to evaluate the efficacy and toxicity of Pacritinib as single agent (Part 1) and Pacritinib + HMA (Part 2) in subjects with lower-risk myelodysplastic syndrome. The primary efficacy outcome of both parts is the overall response rate (ORR) based mainly on hematologic improvement defined by IWG-2006 criteria, and which also includes complete remission (CR), partial remission (PR) and marrow complete remission. In Part 1, patient's overall response will be assessed after 1 cycle of treatment but no more than after 4 cycles of treatment; cycle length is 28 days. If no response is attained after 4 cycles of treatment or if progression occurs during therapy at any time, the patient is eligible to continue on Pacritinib + HMA (Part 2). Part 2 will not continue if Part 1 is stopped early. A maximum of 40 total evaluable patients (n=40) will be enrolled.

Study design: Part 1

The standard practice is to put these patients on observation, an ORR rate of about 15% is clinically relevant. The target ORR with the experimental treatment is 15%. The regimen of the Pacritinib will be considered worthy of further investigation if it elicits an increase in ORR to 15% with acceptable toxicity. A >15% therapy related non-hematological grade 3/4 toxicity rate is considered unacceptable. Thus, interim monitoring rules, assuming the prior distributions below, were constructed that meet the following two conditions,

- 1) Stop if $\text{Prob}\{p(\text{ORR}, E) < 0.15 \mid \text{data}\} > 0.975$, or
- 2) Stop if $\text{Prob}\{p(\text{TOX}, E) > 0.15 \mid \text{data}\} > 0.975$,

where $P(\text{ORR}, E)$ and $P(\text{TOX}, E)$ are the true ORR and toxicity rates for the Pacritinib, and $p(\text{ORR}, H)$ is the true ORR rate of the standard treatment. The first rule provides for stopping the study if the data suggest that it is unlikely (i.e., probability < 2.5%) that ORR rate of the Pacritinib treatment is greater than 15.0%. The second condition will stop the study early if excessive therapy-related non-hematological grade 3/4 toxicity (>15%) is highly probable (i.e., probability >97.5%) for the Pacritinib. Monitoring for toxicity and futility will not begin until 5 patients have been evaluated, and cohort size for future evaluations is 5.

The monitoring rule for the toxicity rate, based on these assumptions and monitoring conditions above is found in Table 11. For example, accrual will cease if 4 or more patients experience toxicities among the first 5 patients.

Table 11. Stop accrual if the number of drug-related non-hematological grade 3/4 toxicities is greater than or equal to indicated (i.e., # patients with toxicities) among the number of patients evaluated								
# patients evaluated	5	10	15	20	25	30	35	40
# patients with toxicities	4-5	5-10	6-15	7-20	8-25	10-30	11-35	Always stop with this many patients

Monitoring the ORR rate, based on the above assumptions and monitoring conditions is found in Table 12. For example, accrual will cease if 0 patients experience an overall response within 4 cycles in the first 15 patients treated.

Table 12. Stop accrual if the number with overall response is less than or equal to indicated (i.e., # patients with overall response) among the number of patients evaluated					
# patients evaluated	5-10		15-25	30-35	40
# patients with overall response	Never Stop with this many patients		0	0-1	Always stop with this many patients

Multc Lean Desktop (version 2.1.0) was used to generate the toxicity and futility stopping boundaries and the OC table (Table 13). In order to utilize the software for the design, a response constant rate of 0.15 and beta (0.3, 1.7) priors were assumed for the standard treatment response distribution and experimental treatment response prior distribution, respectively. In addition, a 15% toxicity constant rate and beta (0.3, 1.7) priors were assumed for the standard treatment toxicity constant rate and experimental treatment toxicity prior distribution, respectively.

The probability of stopping the study early if the true ORR of the Pacritinib was 15% and the true toxicity rate was 15% was 21.9%. Probabilities of stopping early for high true toxicity rates (i.e., 40%) were 95.3% when the true ORR was 15%, and 94.4% when true ORR rate was 30%.

Table 13. Operating characteristics for simultaneous monitoring response and toxicity rates for patients treated with Pacritinib treatment

True Toxicity Rate	True ORR	Prob(stop the trial early)
0.05	0.05	0.6908
	0.10	0.3528
	0.15	0.1654
	0.20	0.0754
	0.25	0.0338
	0.30	0.0150
0.10	0.05	0.6944
	0.10	0.3603
	0.15	0.1750
	0.20	0.0861
	0.25	0.0450
	0.30	0.0264
0.15	0.05	0.7109
	0.10	0.3947
	0.15	0.2194
	0.20	0.1352
	0.25	0.0964
	0.30	0.0787
0.20	0.05	0.7533
	0.10	0.4836
	0.15	0.3341
	0.20	0.2623
	0.25	0.2292
	0.30	0.2141
0.30	0.05	0.8956
	0.10	0.7815
	0.15	0.7182
	0.20	0.6879
	0.25	0.6378
	0.30	0.6675
0.40	0.05	0.9826
	0.10	0.9635
	0.15	0.9529
	0.20	0.9478
	0.25	0.9455
	0.30	0.9444
0.50	0.05	0.9990
	0.10	0.9979
	0.15	0.9973
	0.20	0.9970
	0.25	0.9969
	0.30	0.9968

Study design: Part 2

The standard practice is to put these patients on observation, an ORR rate of about 30% is

clinically relevant. The target ORR with the experimental treatment is 30%. The regimen of the Pacritinib + HMA will be considered worthy of further investigation if it elicits an increase in ORR to 30% with acceptable toxicity. A >30% therapy related non-hematological grade 3/4 toxicity rate is considered unacceptable. Thus, interim monitoring rules, assuming the prior distributions below, were constructed that meet the following two conditions,

- 1) Stop if $\text{Prob}\{p(\text{ORR}, E) < 0.30 \mid \text{data}\} > 0.975$, or
- 2) Stop if $\text{Prob}\{p(\text{TOX}, E) > 0.30 \mid \text{data}\} > 0.95$,

where $P(\text{ORR}, E)$ and $P(\text{TOX}, E)$ are the true ORR and toxicity rates for the Pacritinib + HMA, and $p(\text{ORR}, H)$ is the true ORR rate of the standard treatment. The first rule provides for stopping the study if the data suggest that it is unlikely (i.e., probability < 2.5%) that ORR rate of the Pacritinib + HMA treatment is greater than 30.0%. The second condition will stop the study early if excessive therapy-related non-hematological grade 3/4 toxicity (>30.0%) is highly probable (i.e., probability >95.0%) for the Pacritinib + HMA. Monitoring for toxicity and futility will not begin until 5 patients have been evaluated, and cohort size for future evaluations is 5. The monitoring rule for the toxicity rate, based on these assumptions and monitoring conditions above is found in Table 14. For example, accrual will cease if 4 or more patients experience toxicities among the first 5 patients.

Table 14. Stop accrual if the number of drug-related non-hematological grade 3/4 toxicities is greater than or equal to indicated (i.e., # patients with toxicities) among the number of patients evaluated								
# patients evaluated	5	10	15	20	25	30	35	40
# patients with toxicities	4-5	6-10	8-15	10-20	12-25	14-30	16-35	Always stop with this many patients

Monitoring the ORR rate, based on the above assumptions and monitoring conditions is found in Table 15. For example, accrual will cease if 0 patients experience an overall response within 4 cycles in the first 10 patients treated.

Table 15. Stop accrual if the number with overall response is less than or equal to indicated (i.e., # patients with overall response) among the number of patients evaluated								
# patients evaluated	5	10	15	20	25	30	35	40
# patients with	Never stop	0	0-1	0-2	0-3	0-4	0-5	Always stop

overall response	with this many patients							with this many patients
------------------	-------------------------------	--	--	--	--	--	--	-------------------------------

Multic Lean Desktop (version 2.1.0) was used to generate the toxicity and futility stopping boundaries and the OC table (Table 16). In order to utilize the software for the design, a response constant rate of 0.30 and beta (0.6, 1.4) priors were assumed for the standard treatment response distribution and experimental treatment response prior distribution, respectively. In addition, a 30% toxicity constant rate and beta (0.6, 1.4) priors were assumed for the standard treatment toxicity constant rate and experimental treatment toxicity prior distribution, respectively.

The probability of stopping the study early if the true ORR of the Pacritinib + HMA was 30% and the true toxicity rate was 30% was 14.3%. Probabilities of stopping early for high true toxicity rates (i.e., 50%) were 84.4% when the true ORR was 30%, and 83.6% when true ORR rate was 40%.

Table 16 Operating characteristics for simultaneous monitoring response and toxicity rates for patients treated with Pacritinib treatment		
True Toxicity Rate	True ORR	Prob(stop the trial early)
0.10	0.10	0.9090
	0.20	0.3994
	0.30	0.0848
	0.40	0.0127
	0.50	0.0020
0.20	0.10	0.9103
	0.20	0.4079
	0.30	0.0979
	0.40	0.0268
	0.50	0.0163
0.30	0.10	0.9202
	0.20	0.4730
	0.30	0.1970
	0.40	0.1337
	0.50	0.1243
0.40	0.10	0.9505
	0.20	0.6734
	0.30	0.5023
	0.40	0.4631

	0.50	0.4573
0.50	0.10	0.9849
	0.20	0.9005
	0.30	0.8484
	0.40	0.8365
	0.50	0.8347

Statistical Analysis Plan

All patients who received any dose of the study agent will be included in the analysis for efficacy and safety. Demographic/clinical characteristics (i.e. including duration of response) and safety data of the patients will be summarized using descriptive statistics such as mean, standard deviation, median and range. For the primary efficacy analysis, we will estimate the ORR for the Pacritinib and Pacritinib + HMA, along with the 95% confidence interval. Patients who drop out of the study before completing all the cycles will be treated as “failures” for the primary analysis. Overall response rate (ORR) during the study period will also be presented with the 95% confidence interval. The association between ORR and patient’s clinical characteristics will be examined by Wilcoxon’s rank sum test or Fisher’s exact test, as appropriate. Toxicity type, severity and attribution will be summarized for each patient using frequency tables. The distribution of time-to-event endpoints (EFS and OS) including overall survival and event free survival will be estimated using the method of Kaplan and Meier. Comparisons of time-to-event endpoints by important subgroups will be made using the log-rank tests. The additional treatment in part 2 will be included in time-to-event analysis as time-dependent covariates.

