1.2.1.2 Deaths and Withdrawal from Study Treatment Due To Adverse Events

Phase 1

Three deaths were reported in the phase 1 portion. All were due to an AE/SAE, but no deaths were related to study drug (AML, pneumonia and acute renal failure). Seven patients discontinued treatment due to an AE/SAE.

Phase 2- In phase 2, 5 deaths were reported, 2 due to disease progression and 3 due to an AE/SAE. One death was considered possibly related to pacritinib (subdural hematoma); the

other 2 were considered not related (septic shock, sepsis). Nine patients discontinued treatment due to an AE/SAE.

Serious Adverse Events

Phase 1- 22 SAEs were reported in 8 patients. Of these, 3 related SAEs were reported for 2 patients, including anemia (100 mg), dehydration (600 mg), and soft tissue infection (600 mg). The other SAEs reported during phase 1 were splenic infarction, abdominal pain, gastrointestinal hemorrhage, esophageal varices hemorrhage, anal abscess, cellulitis, orchitis, pneumonia, electrolyte imbalance, fluid imbalance, acute myeloid leukemia, acute renal failure, urinary retention, skin ulcer, hematoma, and peripheral vascular disorder.

Phase 2- 33 SAEs were reported for 14 patients. Of these, 11 SAEs in 7 patients were considered probably related to pacritinib, including one each of the following: hyperbilirubinemia, dehydration, thrombocytopenia, subdural hematoma, anticoagulation drug level above therapeutic, myocardial infarction, hyponatremia, hyperuricemia, septic shock, hypersensitivity, and febrile neutropenia. The other SAEs reported during phase 2 were anemia, atrial fibrillation, atrial flutter, cardiac failure congestive, gastrointestinal hemorrhage, abdominal pain, pyrexia, cellulitis, pneumonia, sepsis, spinal compression fracture, tibia fracture, traumatic brain injury, renal cell carcinoma, pulmonary embolism, pulmonary hypertension, pulmonary infarction, and deep vein thrombosis.

Adverse Events

Phase 1- The observed DLTs included intermittent diarrhea, nausea, fatigue, and dehydration (all occurred at 600 mg). The MTD was determined to be 500 mg daily. The recommended phase 2 dose was 400 mg.

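### The toxicity stopping rules of both parts count grade 3/4 events only, so a patient whose sole qualifying event is a related death is missed

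*Combined protocol and SAP*

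**What the plan says.** In Section 12.0, Part 1, the limit reads "A >15% therapy related non-hematological grade 3/4 toxicity rate is considered unacceptable". The stopping condition acts when "excessive therapy-related non-hematological grade 3/4 toxicity (>15%) is highly probable (i.e., probability >97.5%) for the Pacritinib". Table 11 turns this into counts under the title "Stop accrual if the number of drug-related non-hematological grade 3/4 toxicities is greater than or equal to indicated".

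Part 2 has the same structure. The limit is "A >30% therapy related non-hematological grade 3/4 toxicity rate is considered unacceptable", the condition acts when "excessive therapy-related non-hematological grade 3/4 toxicity (>30.0%) is highly probable (i.e., probability >95.0%) for the Pacritinib + HMA", and Table 14 carries the same title wording as Table 11.

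Section 13.0 grades adverse events by CTCAE version 4.0. Elsewhere death appears in four ways:

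- in Section 13.0, as a serious adverse event to be reported;
- in Section 10.0, Table 9, as a response failure when it occurs during treatment;
- in the survival definitions of Table 9;
- in the survival analyses of the Statistical Analysis Plan paragraph of Section 12.0.

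None of these adds a death to the toxicity count, and there is no separate stopping rule for related deaths.

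**The concern.** The event that drives a participant-protection rule leaves out the worst outcome on its own scale. Two patients can have the same related event. If one survives it at grade 4 and the other dies of it, only the survivor moves the trial toward stopping.

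A related death is not a remote idea for this drug. Section 1.2.1.2 of the background says of an earlier phase 2 cohort: "One death was considered possibly related to pacritinib (subdural hematoma"). Part 2 then adds a hypomethylating agent, and the documents give no safety experience with that combination.

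At stake is the chance that accrual stops when the true rate of severe or fatal related toxicity is too high.

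**Working it through.** **Inputs (Section 12.0).** Part 1: limit 0.15, cutoff 0.975, prior from "a 15% toxicity constant rate and beta (0.3, 1.7) priors were assumed for the standard treatment toxicity constant rate", that is Beta(0.3, 1.7). Part 2: limit 0.30, cutoff 0.95, prior from "a 30% toxicity constant rate and beta (0.6, 1.4) priors were assumed for the standard treatment toxicity constant rate", that is Beta(0.6, 1.4). Looks take place at 5, 10, ..., 35 patients.

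**Step 1: reproduce the plan's boundaries.** With x toxicities in n patients the posterior is Beta(a + x, b + n − x). The boundary is the smallest x for which P(rate > limit) exceeds the cutoff. For example, in Part 1 at n = 10, x = 4 gives 0.954 (continue) and x = 5 gives 0.990 (stop), so the boundary is 5. Over all looks:

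- Part 1: 4, 5, 6, 7, 8, 10, 11, exactly as in Table 11.
- Part 2: 4, 6, 8, 10, 12, 14, 16, exactly as in Table 14.

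The boundaries depend only on limit, prior and cutoff. They do not depend on which grades make up the event.

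**Step 2: one missed death at the first look, Part 1.** Three of the first 5 patients have a related grade 3/4 event and a fourth has a related death only.

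- As written, x = 3: P(rate > 0.15) under Beta(3.3, 3.7) is 0.973, below 0.975, so accrual continues.
- Death counted, x = 4: P(rate > 0.15) under Beta(4.3, 2.7) is 0.997, so accrual stops.

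At the extreme, four deaths among 5 patients with no earlier grade 3/4 event give x = 0 and a posterior of 0.080. Counted, they give x = 4 and 0.997.

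**Step 3: effect over the trial.** The stop probability is exact: the toxicity count is built up in binomial steps of 5, and paths that reach a boundary are removed at each look. Only the toxicity rule is applied. As a check, Part 2 at a true rate of 50% gives 0.8345. Table 16 shows 0.8347 at 50% toxicity and 50% ORR, where futility adds almost nothing. Table 13 gives no such anchor for Part 1: at 15% toxicity and 15% ORR it states 0.2194, while Tables 11 and 12 give 0.147. The Part 1 figures below therefore rest on Table 11's boundaries.

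The documents state no rate of fatal related toxicity, so the share of patients with a grade 5 event only is an assumption, shown over a range. The monitored rate is the true grade 3-5 rate minus that share.

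| Grade-5-only share (points) | Part 1 monitored rate (true 30%) | Part 1 P(stop) | Part 2 monitored rate (true 50%) | Part 2 P(stop) |
|---|---|---|---|---|
| 0 (all events counted) | 30% | 0.612 | 50% | 0.835 |
| 0.5 | 29.5% | 0.589 | 49.5% | 0.820 |
| 1 | 29% | 0.565 | 49% | 0.806 |
| 5 | 25% | 0.371 | 45% | 0.665 |

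**The case against.** Several points on the other side are fair.

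- **Deaths are not invisible to all stopping.** A reader might infer that a related death counts toward no stopping rule. That goes too far: Table 9 makes death during treatment a failure, and the Statistical Analysis Plan treats early drop-outs as failures, so a death before response is a non-response for Tables 12 and 15. This stands, but it is a weak substitute. Table 12 cannot stop Part 1 before 15 patients, and then only with no responders, and it measures lack of efficacy rather than harm.
- **Not every related death is missed.** Tables 11 and 14 count patients. A patient with an earlier related non-hematological grade 3/4 event is already in the count. This stands and limits the gap to patients whose only qualifying event is grade 5.
- **The final safety summary is not affected.** It is tempting to add that the final toxicity rate leaves fatal events out. The plan does not support this: toxicity is tabulated by type, severity and attribution with no grade limit, and no final test against 15% or 30% is defined.
- **Fatal related toxicity looks uncommon.** The background reports 191 exposed patients. The death described there as possibly related gives 1/191 = 0.5% (exact 95% upper limit 2.9%). This is why the 5-point row is a high assumption. It is not a firm bound: nine deaths in the two 2007 studies had unknown cause (3 + 5 + 1), and nothing is known about the combination.
- **The wording may be shorthand.** Section 13.0 also says grade 3 or 4 for data entry, although deaths must obviously be recorded. Against this, the Duration of Therapy text in Section 4.0 writes grade ≥ 3, so the open-ended form was available. Intent cannot be settled from the text.
- **Fatal events are reported quickly.** Unexpected related fatal events go to the IND Office within 24 hours and all serious events within 5 working days. No passage links those reports to accrual.
- **The first-look example is close to the cutoff** (0.973 against 0.975). This is true, and it is offered as an illustration only.

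**Conclusion.** The point holds in a limited form. Under the toxicity rules of both parts, as written, a patient whose only qualifying event is a related non-hematological death is not counted. No other passage repairs this.

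The size depends on an assumed rate. With 0.5 to 1 percentage point of grade-5-only events, the loss in stop probability is about 0.02 to 0.05 in Part 1 (true rate 30%) and 0.01 to 0.03 in Part 2 (true rate 50%). With 5 points it is about 0.24 and 0.17. These figures assume independent patients, the printed boundaries and the toxicity rule acting alone. That a fatal event is grade 5 comes from the CTCAE scale the protocol adopts, since the protocol does not print the grades.

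The case for change rests on the definition more than on the expected numbers: a safety rule should not depend on a guess that 3/4 was meant to include fatal events.

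**What to change.** In Section 12.0, replace the grade 3/4 wording with drug-related non-hematological toxicity of grade 3 or higher (grades 3-5, including related death). The places are the limit and the verbal stopping condition of each part and the titles of Tables 11 and 14. Align the data-entry sentence in Section 13.0 so that related grade 5 events are clearly captured in the database that feeds the monitoring.

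Priors, cutoffs and the boundaries in Tables 11 and 14 stay as they are. Tables 13 and 16 are indexed by the true rate of the counted event, so this change alone does not require them to be recalculated; they would simply be read at the grade 3-5 rate. The cost is a wording amendment and, if related deaths occur, a somewhat higher toxicity count at the looks. If grade 3 or higher was always intended, the amendment only says so.

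### Part 1's Table 13 and the quoted 21.9%, 95.3% and 94.4% do not follow from 5-patient monitoring; they match looks every 4 patients, and the specified design stops less often than stated.

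*Combined protocol and SAP*

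**What the plan says.** All references are to section 12.0, Statistical Considerations, Study design: Part 1.

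- Schedule: "Monitoring for toxicity and futility will not begin until 5 patients have been evaluated, and cohort size for future evaluations is 5". The maximum is 40: "A maximum of 40 total evaluable patients (n=40) will be enrolled".
- Futility: stop when "it is unlikely (i.e., probability < 2.5%) that ORR rate of the Pacritinib treatment is greater than 15.0"%.
- Toxicity: stop when "excessive therapy-related non-hematological grade 3/4 toxicity (>15%) is highly probable (i.e., probability >97.5%) for the Pacritinib".
- Response inputs: "a response constant rate of 0.15 and beta (0.3, 1.7) priors were assumed for the standard treatment response distribution" and the experimental prior. Toxicity inputs: "a 15% toxicity constant rate and beta (0.3, 1.7) priors were assumed for the standard treatment toxicity constant rate" and the experimental prior.
- Table 11 stops for toxicity at 4/5, 5/10, 6/15, 7/20, 8/25, 10/30 and 11/35 or more. Table 12 stops for futility at 0 responses with 15 to 25 patients and at 0 or 1 with 30 to 35.
- The text attributes both the boundaries and Table 13 to the same software. It then gives the early-stopping probability "if the true ORR of the Pacritinib was 15% and the true toxicity rate was 15% was 21.9"%, and for high toxicity "i.e., 40%) were 95.3% when the true ORR was 15%, and 94.4% when true ORR rate was 30"%. These three figures agree with Table 13 (0.2194, 0.9529, 0.9444).

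**The concern.** Tables 11 and 12 and Table 13 should describe one design. If Table 13 came from a different look schedule, the protocol credits Part 1 with stopping probabilities it does not have. Table 13 is the only quantitative account of how the Part 1 rules perform, and an ethics committee or monitoring body would rely on it to judge how well patients are protected from a toxic or inactive regimen. It also bears on Part 2, because section 12.0 (General Description) says Part 2 will not continue if Part 1 stops early.

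**Working it through.** **1. Boundaries.** After x events in n patients the posterior is Beta(0.3 + x, 1.7 + n − x), compared with 0.15 at cutoff 0.975.

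- Futility: Pr(ORR < 0.15) is 0.9732 at 0/10 (continue) and 0.9902 at 0/15 (stop). It is 0.9727 at 1/25 (continue) and 0.9873 at 1/30 (stop).
- Toxicity: Pr(TOX > 0.15) is 0.9732 at 3/5 (continue) and 0.9972 at 4/5 (stop). It is 0.9732 at 10/35 (continue) and 0.9899 at 11/35 (stop).

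Looks at 5, 10, ..., 35 reproduce Tables 11 and 12 exactly, so the inputs are read correctly.

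**2. Formula.** With response and toxicity independent, P(stop early) = 1 − P(no futility stop) × P(no toxicity stop). Each factor is an exact binomial recursion over the looks. Reaching 40 is the end of the trial, not an early stop.

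**3. Toxicity 15%, ORR 15%, looks every 5 (as specified).**

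- A futility stop occurs at 15 patients with no response, or at 30 with exactly one response, in the first 15: 0.85^15 + 15 × 0.15 × 0.85^29 = 0.0874 + 0.0202 = 0.1076. P(no futility stop) = 0.8924.
- Toxicity stops over the seven looks total 0.0443. P(no toxicity stop) = 0.9557.
- P(stop early) = 1 − 0.8924 × 0.9557 = **0.1471**.

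**4. The same scenario, looks every 4.** The same rule gives toxicity boundaries 3/4, 4/8, 5/12, 6/16, 7/20, 8/24, 9/28, 10/32 and 11/36. Futility stops at 0 with 12 to 24 patients and at 0 or 1 with 28 to 36.

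- Futility: 0.85^12 + 12 × 0.15 × 0.85^27 = 0.1422 + 0.0224 = 0.1646. P(no futility stop) = 0.8354.
- Toxicity stops total 0.0656. P(no toxicity stop) = 0.9344.
- P(stop early) = 1 − 0.8354 × 0.9344 = **0.2194**, the printed figure.

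**5. Toxicity 40%.** P(no toxicity stop) is 0.0743 with looks every 5 and 0.0564 with looks every 4.

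- ORR 15%: 1 − 0.8924 × 0.0743 = 0.9337 (every 5); 1 − 0.8354 × 0.0564 = 0.9529 (every 4, as printed).
- ORR 30%: 1 − 0.9951 × 0.0743 = 0.9261 (every 5); 1 − 0.9859 × 0.0564 = 0.9444 (every 4, as printed).

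**6. Selected scenarios from Table 13.**

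| Toxicity / ORR | Printed | Looks every 5 | Gap (points) |
|---|---|---|---|
| 5% / 5% | 0.6908 | 0.6328 | 5.8 |
| 5% / 10% | 0.3528 | 0.2767 | 7.6 |
| 15% / 15% | 0.2194 | 0.1471 | 7.2 |
| 20% / 10% | 0.4836 | 0.3940 | 9.0 |
| 20% / 15% | 0.3341 | 0.2524 | 8.2 |
| 30% / 15% | 0.7182 | 0.6535 | 6.5 |
| 40% / 15% | 0.9529 | 0.9337 | 1.9 |
| 40% / 30% | 0.9444 | 0.9261 | 1.8 |

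All 42 printed values exceed the 5-patient values (median gap 4.0 points). Adding a look at 40 does not remove the discrepancy (largest gap 6.0 points). Looks every 4 match 41 of 42 cells to four decimals. Of cohort sizes 1 to 10 no other fits; the next closest, 6, is off by up to 4.0 points.

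**7. The odd cell.** Toxicity 0.30 / ORR 0.25 is printed as 0.6378, below the 0.6675 printed for ORR 0.30. At fixed toxicity, early stopping cannot rise as ORR improves. The 4-patient value is 0.6738, so the digits look transposed.

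**8. Control.** The same code with Part 2's inputs and 5-patient looks reproduces all 25 cells of Table 16 within 0.00005. This supports the independence assumption and the treatment of n = 40. A 200,000-run simulation of Part 1 also agrees (0.146 at 15%/15%; 0.935 at 40% toxicity and 15% ORR).

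**The case against.** The strongest reply is that nothing operative is wrong. Accrual is governed by the posterior criteria and Tables 11 and 12, which are mutually consistent. Correcting Table 13 changes no boundary, sample size or estimate. That is true, but the protocol still states stopping probabilities that its design does not have.

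The error is also uneven. Fifteen of the 42 cells differ by 2 points or less, including all 12 at toxicity 40% and 50%, and stopping at those rates remains at least 92.6%. This stands: the material gaps are at toxicity of 30% or less, mostly with low to moderate ORR. Nor is every correction unfavourable, since fewer wrongful stops at 15%/15% count in the design's favour.

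Finally, no section mentions cohorts of 4. That origin is an inference from the numerical match, as is the digit transposition. The finding does not depend on either, because Table 13 fails under the stated schedule whatever its source.

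**Conclusion.** The point holds. Under the specified 5-patient looks, Table 13 overstates early stopping in every scenario, by up to 9.0 points, and the headline 21.9% should be 14.7%. At twice the toxicity limit (30%) with ORR 15%, the chance of not stopping early is about 35% (1 − 0.6535) rather than 28% (1 − 0.7182). The chance of stopping a safe but inactive drug (5%/5%) is 63.3%, not 69.1%.

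The conclusion rests on the stated priors, reference rates and cutoffs, independence of response and toxicity, and no early stop counted at 40; the exact match to Table 16 supports the last two. The cohort-size error is confined to Part 1. Separately, the Part 2 text quotes 14.3% and 84.4% where Table 16 prints 0.1970 and 0.8484, and that needs its own correction.

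**What to change.** Keep the 5-patient schedule and Tables 11 and 12, and replace Table 13 with:

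| Toxicity | ORR 0.05 | 0.10 | 0.15 | 0.20 | 0.25 | 0.30 |
|---|---|---|---|---|---|---|
| 0.05 | .6328 | .2767 | .1077 | .0400 | .0144 | .0050 |
| 0.10 | .6348 | .2806 | .1126 | .0452 | .0198 | .0105 |
| 0.15 | .6490 | .3086 | .1471 | .0823 | .0579 | .0489 |
| 0.20 | .6924 | .3940 | .2524 | .1957 | .1743 | .1664 |
| 0.30 | .8574 | .7191 | .6535 | .6272 | .6173 | .6137 |
| 0.40 | .9727 | .9462 | .9337 | .9287 | .9268 | .9261 |
| 0.50 | .9982 | .9964 | .9955 | .9952 | .9951 | .9950 |

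Change the three percentages in the text to 14.7%, 93.4% and 92.6%. If 4-patient cohorts were intended, change the schedule sentence and Tables 11 and 12 to the step 4 boundaries instead, and correct the 0.6378 cell to 0.6738.

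The cost of the first option is one software rerun, one table and three numbers. Sample size and thresholds do not change. The stated protection against a toxic or inactive regimen becomes somewhat weaker, and the stated risk of wrongly stopping at target becomes smaller.
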